**Table 7: Study Groups and Number of Subjects** 

	TTHX1114	4 Regimen		
	Day	Dose	Number of Subjects	
Group 1	N/A	N/A	8 (Closed after 1 enrolled)	
	Day -3	10ng		
	Day 0	50ng	9.16	
Group 2	Day 7	10ng	8-16 (Closed after 9 enrolled)	
•	Day 14	10ng		
	Day 21	10ng		
Group 3	Day 0	100ng	20	
Group 4	Day 0	100ng	20	
	Day 7	30 or 50ng		
	Day 14	30 or 50ng		
	Day 21	30 or 50ng		
Group 1a	Weekly x 5	30 or 50ng	NA	
Group 3a	Weekly x4	30 or 50ng	NA	
·		 	up to 50	

[figure not shown]
Subject will be consented and screened for eligibility during the screening period prior to the scheduled DWEK/DSO procedure.

The study schema is presented in Figure 1 and Figure 2.

Confidential and Proprietary

Amendment 7.0: September 22, 2022

Figure 1: Study Treatment Schema

\*Subjects who have not sufficiently recovered by Day 28, may receive an additional dose of TTHX1114 following discussion with the Medical Monitor

Eligible subjects who do not wish to receive investigational product or who do not have a qualifying Fellow Eye will be assigned to Treatment Group 1.

Following preliminary safety and tolerability assessment of the 50ng IC injection in Group 2, Trefoil may elect to open Group 3 and Group 4

[figure not shown]
- Group 3 in which eligible subjects will be given a "1 and done" dosing regimen in which TTHX1114 will be administered as a 100ng/100mcL volume injection at the time of DWEK/DSO
- Group 4 in which eligible subjects will be given a 100ng/100mcL volume injection at the time of DWEK/DSO and then weekly injections of 30 or 50ng (30 or 50mcL) x3. Subjects in Group 4, who have not sufficiently recovered by Day 28, may receive an additional dose of TTHX1114 following discussion with the Medical Monitor

Following preliminary safety and efficacy evaluation in subjects who received TTHX1114, Trefoil may open enrollment in Groups 1a and 3a in which TTHX1114-naive subjects in Group 1 and subjects in Group 3 may be allowed to "roll-over" to a TTHX1114 regimen of up to 5 weekly injections of TTHX1114. To be eligible for Group 1a or Group 3a, subjects must continue to be eligible for the study (e.g., have a suitable fellow eye and not have had any severe suspected adverse reactions.

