# 4.1 Efficacy Endpoints

Efficacy endpoints in this study include:

- o The number of subjects in each group with 20/40 or better BCVA at Day 28
- Central corneal thickness at Day 28

The following additional endpoints will also be assessed:

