### 8.4 Adverse Events of Special Interest

#### 9. STATISTICS

### 9.1 Sample Size

The sample size for this study was determined by clinical and practical rather than statistical considerations. Sixteen subjects in the active treatment group compared to 8 subjects in the non-treatment control group were planned during the study to provide a preliminary estimate of safety and efficacy.

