#### 9.2 Analyses

The study includes a concurrent non-treatment control group. The active treatment group will be compared to the control group. In addition, descriptive statistics will be used to tabulate and summarize other efficacy variables and safety outcomes. Baseline and demographic characteristics will be presented. Continuous variables will be summarized by descriptive statistics (sample size, mean/ standard deviation, median, minimum and maximum). Discrete variables will be summarized by frequencies and percentages. Ocular AEs involving the study eye will be summarized by presenting the number and percentage of subjects having any ocular AE. Any other information collected (such as severity or relationship to study drug and intracameral injection) will be listed as appropriate.

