**Table 12: Analysis Sets** 

Analysis Set	Description of Population	Reference
Full Analysis Set*	
 
Received any study treatment (at least 1 complete or partial dose)
 
	ICH E9 (5.2.1)
Per Protocol Set	Met all eligibility criteria	ICH E9 (5.2.2)
	Have received all study treatments per protocol	
	
 
Underwent DWEK/DSO of 4 to 5mm
 
	
	
 
Have sufficient data collected for the accurate assessment of study endpoints
 
	

\*The Full Analysis Set will be used for the Safety Population

The Per Protocol Population will be used to assess the primary and secondary efficacy endpoints compared to the control group.

The Safety Population set includes all participants in participants who received any TTHX1114 and will be the population for safety outcomes; this population will be compared with the control group. Ocular AEs involving the study eye will be tabulated. Ocular AEs for the fellow eye and non-ocular AEs will be provided as a listing.

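### Sections 9.2 and 9.3.1 keep two-group wording for a study with at least three TTHX1114 regimens: the visible text requires neither adverse events nor corneal thickness by regimen and prespecifies no between-regimen estimate

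*Combined protocol and SAP*

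**What the plan says.** - Section 9.1 describes a two-group study: "Sixteen subjects in the active treatment group compared to 8 subjects in the non-treatment control group were planned during the study". It adds that "The sample size for this study was determined by clinical and practical rather than statistical considerations".
- Section 9.2 follows that layout: "The active treatment group will be compared to the control group". Other efficacy and safety variables get descriptive summaries, with no statement about display by regimen.
- Section 9.3.1 (Table 12 and the text below it) defines the safety population as those "who received any TTHX1114 and will be the population for safety outcomes; this population will be compared with the control group". Per Protocol efficacy is also assessed only against control.
- Section 4, Table 7, lists Group 1 (control, closed after 1 enrolled), Group 2 (closed after 9), Group 3 (20), Group 4 (20) and roll-over Groups 1a and 3a. Group 3 receives a single 100 ng injection at surgery. The text reads: "Group 4 in which eligible subjects will be given a 100ng/100mcL volume injection at the time of DWEK/DSO and then weekly injections".
- Section 4.1 gives one endpoint by group: "The number of subjects in each group with 20/40 or better BCVA at Day 28". Day 28 CCT is listed next to it without that qualifier. The list of additional endpoints is not visible in this copy.
- Section 9.3 leaves the detail to a statistical analysis plan to be written before database lock. No text of that plan is in the file.

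**The concern.** The analysis section was written for one active arm and was not brought into line with Table 7. Taken literally, it puts three regimens into one group that describes no treatment any subject received.

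Safety is the weaker spot. Scheduled injections range from 1 to 5 per subject, so a harm linked to repeated injection would fall mainly on the weekly groups and be diluted by the single-injection group. Nothing visible requires adverse events by regimen.

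With one control subject, the comparison that Section 9 does name carries almost no information. The Group 4 versus Group 3 difference is the least weak comparison left, and it is not prespecified. The study is open label and the analysis plan is due only before lock, so a contrast chosen late could be chosen with the results known.

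**Working it through.** **Inputs.** Doses, injection counts and group sizes come from Table 7. Event rates, a two-sided 5% level and full enrolment with no exclusions are assumptions. The documents give no rate, standard deviation (SD), alpha or power, so the 16 versus 8 in Section 9.1 cannot be reproduced, and the plan does not claim a statistical basis for it. The Table 7 total does reproduce: 1 + 9 + 20 + 20 = 50.

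**1. Regimens covered by the single active group**

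| Group | Scheduled injections | Total dose | n |
|---|---|---|---|
| 2 | 5 | 10 + 50 + 3×10 = 90 ng | 9 |
| 3 | 1 | 100 ng | 20 |
| 4 | 4 | 100 + 3×30 = 190 ng to 100 + 3×50 = 250 ng | 20 |

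Three is a minimum. Group 4 allows two weekly dose levels and a possible further injection, and Groups 1a and 3a add more.

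**2. The comparison as written.** The pooled group is 9 + 20 + 20 = 49 against 1 control. The smallest two-sided Fisher p-value that can occur is 1/50 = 0.02. The difference detectable with 80% power is (1.96 + 0.84) × √(1/49 + 1), about 2.8 SD.

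**3. What pooling does to safety rates.** Pooled rate = Σ(n × rate)/49.
- Assumed 5%, 5%, 30% in Groups 2, 3, 4: (0.45 + 1.0 + 6.0)/49 = 15%, half the Group 4 rate and three times the Group 3 rate.
- If Group 2, with 5 injections, also had 30%: (2.7 + 1.0 + 6.0)/49 = 20%, which is again no group's rate.
- With no events at all, the one-sided 95% upper bound is 1 − 0.05^(1/n): 5.9% for n = 49, 13.9% for n = 20 and 28.3% for n = 9. The pooled figure overstates what is known about any one regimen.

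**4. What Group 4 minus Group 3 could show at 20 per group**
- 20/40 proportion, Newcombe 95% interval from the two Wilson intervals. For 14/20 versus 8/20 the Wilson intervals are 0.481 to 0.855 and 0.219 to 0.613. Lower limit: 0.30 − √[(0.70 − 0.481)² + (0.613 − 0.40)²] = −0.006. Upper limit: 0.30 + √[(0.855 − 0.70)² + (0.40 − 0.219)²] = 0.538. That is about −1 to +54 points. For 10/20 versus 10/20 it is ±28 points.
- CCT: half-width of the 95% interval = 2.024 × √(2/20) = 0.64 SD.
- As a test, Fisher power is 16% for 50% versus 70%, 41% for 50% versus 80% and 74% for 50% versus 90%.

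**5. Are the two groups comparable?** They share the Day 0 injection, the planned size and the main visit days. They differ in four ways that the estimate must handle:
- Section 4 assigns subjects to whichever group is open.
- Section 5 lets subjects who received active drug in TTHX-001 enter Group 3, and names no other group for them.
- Section 6.1.2 lets a second eye enter Group 3 or Group 4.
- Section 8.1 reports adverse events until 28 days after each treatment: to Day 0 + 28 = 28 in Group 3, but to Day 21 + 28 = 49 in Group 4. Tables 3 and 4 also differ on eye-pressure checks: Group 4 has pre- and post-injection checks on Days 14 and 21, and Group 3 has none on those days.

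**The case against.** The strongest reply is that the pooling is inferred. The singular wording in Section 9.2 looks like a remnant of the 16 versus 8 plan. Table 12 defines an analysis set, which does not fix the columns of a safety table. The descriptive summaries in Section 9.2 do not rule out display by group. The detailed analysis plan is not in the file, although the document history refers to one, and the additional endpoints are not visible. This stands to the extent that the documents do not show a deliberate choice to pool. It does not remove the problem, because the current text names only pooled comparisons with control and does not require by-regimen safety results.

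Three stronger readings are tempting, and the documents do not support them:
- A reader might infer that Group 4 versus Group 3 will never be analysed. It may be in the analysis plan. All that can be said is that the visible protocol does not prespecify it.
- A reader might infer that pooling hides a difference in the 20/40 rate. Section 4.1 counts that endpoint in each group, so such a difference would be visible. The masking argument applies to adverse events and possibly to CCT.
- A reader might infer that Group 4 versus Group 3 isolates the effect of the weekly injections, or is the one contrast the design supports. Allocation by open group, prior exposure and second eyes all prevent that.

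It is also fair to say that choosing between regimens is not a stated objective and that 20 per group gives low power. Both count against a hypothesis test. Neither counts against a labelled estimate with its interval.

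**Conclusion.** The concern holds as a mismatch between Section 9 and Table 7. The visible text compares one active group with a control group closed after 1 subject, gives only the Day 28 20/40 count by group, and prespecifies no between-regimen estimate. Under the assumed event rates, a pooled safety figure of 15% to 20% would stand for regimens whose true rates are 5% and 30%. The rates are illustrative; that regimens from 1 to 5 injections are mixed comes straight from Table 7.

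Group 4 minus Group 3 is worth prespecifying as the least weak comparison available. It remains non-randomised, open to confounding and imprecise: about ±28 points on the 20/40 proportion and ±0.64 SD on CCT. Those widths assume 20 evaluable subjects per group. Per Protocol exclusions, or restriction to first-treated eyes, would widen them. The change should be made, but the point does not invalidate the study.

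**What to change.** In Sections 9.2 and 9.3.1, and in the analysis plan:

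1. Replace the single active group with separate summaries of efficacy and safety for Groups 2, 3 and 4. Show the roll-over periods (1a, 3a) separately. Keep an all-treated column as a supplement only, for example for rare events.
2. Prespecify Group 4 minus Group 3 as a descriptive, non-randomised estimate: the difference in the Day 28 20/40 proportion with a Newcombe 95% interval, and the difference in Day 28 CCT with a 95% interval. Attach no test.
3. Compare ocular adverse events between these groups only over a common window, for example Day 0 to Day 28, and note that the scheduled eye-pressure checks differ. Events after the window are listed by group.
4. Base the contrast on first-treated eyes, with a sensitivity analysis that excludes subjects who received TTHX1114 in TTHX-001.
5. Show Group 4 by the weekly dose actually received. Table 4 shows 50 ng for the weekly injections, while Table 7 and the Section 4 text allow 30 or 50 ng. These passages must be reconciled before regimens are labelled for analysis.

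**Cost.** Wording and table shells; no new subjects, visits or data. The downside is wide by-regimen intervals, and a contrast that readers may over-interpret unless it is labelled as estimation under non-random assignment. Fixing it before lock prevents a contrast from being chosen after the open-label results are known.

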#### 3. TRIAL OBJECTIVES AND PURPOSE

The primary objective of this clinical trial is to evaluate the safety and efficacy of TTHX1114 in the setting of DWEK/DSO. The primary efficacy endpoint will include CEC counts/ characteristics and BCVA following the surgical procedure.

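### The protocol names one adverse-event statistic, any ocular AE in the study eye; severity, relationship, non-ocular AEs and AEs in a possibly treated fellow eye go to listings, so a specific signal is diluted or left uncounted

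*Combined protocol and SAP*

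**What the plan says.** Section 3 names safety and efficacy together: "The primary objective of this clinical trial is to evaluate the safety and efficacy of TTHX1114 in the setting of DWEK/DSO".

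Section 9.2 gives the AE analysis in two sentences. The first names the statistic: "Ocular AEs involving the study eye will be summarized by presenting the number and percentage of subjects having any ocular AE". The second deals with the rest: "Any other information collected (such as severity or relationship to study drug and intracameral injection) will be listed as appropriate".

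Section 9.3.1, in the text below Table 12, adds: "Ocular AEs involving the study eye will be tabulated". It then says: "Ocular AEs for the fellow eye and non-ocular AEs will be provided as a listing".

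Section 9.2 also has a general sentence that "descriptive statistics will be used to tabulate and summarize other efficacy variables and safety outcomes". Section 9.3 defers a full SAP to before database lock.

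Other sections bear on the point:
- AE terms are coded in MedDRA (8.2.1, 12.3), graded for severity (Table 11) and assessed for causality (8.2.4).
- The stopping rule (4.5) rests on unacceptable toxicity, with frequency and severity of AEs monitored as the study runs.
- The note in Section 4 calls the first treated eye the Study Eye and the contralateral eye the Fellow Eye. Section 6.1.2 allows the contralateral eye to be treated by re-enrolment in Group 3 or 4.

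**The concern.** The sites collect coded terms, severity grades and causality for each event, yet no named table uses them. If the sentences in 9.2 and 9.3.1 are followed as written, the report will show what fraction of subjects had some ocular AE in the first eye, with everything else in line listings. All subjects have eye surgery on Day 0, so that fraction mixes surgical events with any effect of the drug or of the injections.

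The regimens in Table 7 differ in ways a reader will want described: one injection of 100 ng, 100 ng followed by three weekly injections, five injections in Group 2, and the roll-over courses. One any-event percentage per group does not say which events occurred, how severe they were, or how often the investigator attributed them to drug or injection.

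There is also a gap in coverage. A fellow eye that receives TTHX1114 contributes exposure, but its ocular AEs are only listed. They would fall outside every table the protocol names.

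**Working it through.** The documents state no AE rate and no figure on this point, so there is nothing of the plan's own to reproduce. The check has two parts.

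**1. What is tabulated and what is listed**

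| AE data | Treatment in 9.2 / 9.3.1 |
|---|---|
| Any ocular AE, study eye | Number and percentage of subjects |
| Study-eye ocular AEs by term | Tabulated, level not stated |
| Severity, relationship | Listed |
| Ocular AEs, fellow eye (may be treated) | Listed |
| Non-ocular AEs | Listed |

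The last three rows are stated rules, not silences.

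**2. How much an any-event percentage dilutes a specific event**

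Inputs, all assumed:
- b, the proportion of subjects with some other ocular AE, varied from 20% to 95%;
- q, the proportion with the specific event, 5% in one group and 25% in another;
- independence of the two.

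Formula: P(any) = 1 - (1-b)(1-q) = b + (1-b)q. The event adds (1-b)q to the background, and a change in q from 5% to 25% shows as (1-b) × 20 points.

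| b | P(any) at q = 5% | P(any) at q = 25% | Visible change |
|---|---|---|---|
| 20% | 1 - 0.80×0.95 = 24.0% | 1 - 0.80×0.75 = 40.0% | 16 points |
| 50% | 1 - 0.50×0.95 = 52.5% | 1 - 0.50×0.75 = 62.5% | 10 points |
| 80% | 1 - 0.20×0.95 = 81.0% | 1 - 0.20×0.75 = 85.0% | 4 points |
| 90% | 1 - 0.10×0.95 = 90.5% | 1 - 0.10×0.75 = 92.5% | 2 points |
| 95% | 1 - 0.05×0.95 = 95.25% | 1 - 0.05×0.75 = 96.25% | 1 point |

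A count by preferred term shows the full 20 points at every b. Under these assumptions dilution occurs at any background above zero. Its size depends on b.

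**3. What a table by term cannot do**

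For 5% against 25%, a two-sided Fisher test at an assumed 0.05 has about 30% power with 20 per group. With 5% among the 9 subjects of Group 2 and 25% among 20, it has about 7%. For an event not seen in 20 subjects, the exact two-sided 95% upper limit is 1 - 0.025^(1/20) = 16.8%, whichever table is used. Group 1 closed after 1 enrolled (Table 7), so its AE percentage can only be 0% or 100%.

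**The case against.** The strongest reply is that the protocol does not confine itself to the any-event figure. Section 9.2 promises to tabulate and summarise safety outcomes, Section 9.3.1 says study-eye ocular AEs will be tabulated, and a full SAP is still to come, where tables by MedDRA term would be ordinary content. This stands in part. A reader might infer that any ocular AE is the whole of the safety analysis, and the text does not support that: the level of tabulation for the study eye is left open. It does not answer the explicit listing rules for severity, relationship, non-ocular AEs and fellow-eye AEs. In an open-label study, a SAP due only before database lock also lets the choice of AE tables follow sight of the data.

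A reader might also infer that the percentage must be close to 100% after this surgery and so cannot show any drug or injection signal. The documents give no AE rate, and at b = 20% most of the difference remains visible. Some signals also have another route: IOP is measured before and after injections, corneal thickness is scheduled repeatedly, and stromal clarity has a grading scale (6.4.5). Listings for up to 50 subjects can be read, and an event with a true rate of 10% has a 1 - 0.9^49 = 99% chance of appearing at least once among 49 treated subjects. Section 8.4, on AEs of special interest, has no visible text and is not counted as a gap.

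On the fellow eye, Section 6.1.2 also defines the study eye as the one receiving TTHX1114, so a re-enrolled contralateral eye could be read as a study eye. However, the note in Section 4, written to remove that ambiguity, keeps the name Fellow Eye for it, and 6.1.2 uses the same name. The reporting rule should not depend on which reading is taken.

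Finally, the groups are small, non-randomised and differ in several features at once. The Day 0 doses of 50 ng and 100 ng, for example, come with different earlier and later injections. Tables by term will not isolate a dose effect. That stands, and it limits the benefit to description.

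**Conclusion.** The point holds as a weakness in the specified safety reporting. The protocol names one AE statistic, specifies no table by term, severity or relationship, and sends non-ocular AEs and ocular AEs in a possibly treated fellow eye to listings. If those sentences are followed, part of the primary objective is reported without the counts by regimen that the collected data allow.

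The dilution is (1-b) times the true difference: a 20-point difference shows as 10 points at b = 50% and 2 points at b = 90%. This rests on an assumed b and on independence between the specific event and the other ocular AEs. The gap for the fellow eye, and the listing rule for severity and relationship, rest on the text alone.

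The change would improve description across regimens. It would not give a usable test against control or a clean dose comparison.

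**What to change.** In Sections 9.2 and 9.3.1, and in the SAP, replace the any-event and listing-only rule with tables of the number and percentage of subjects, and the number of events:
- by regimen, with the roll-over periods (Groups 1a and 3a) shown separately;
- by MedDRA system organ class and preferred term;
- by worst severity, and by relationship to drug and to injection;
- for ocular AEs in every treated eye, study or fellow, under the regimen that eye received;
- for non-ocular AEs, with a stated rule for assigning a regimen when both eyes were treated.

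Keep the any-event line as the top row and keep the listings. Fix the table list as early as possible, not just before database lock. Exact confidence intervals for selected terms and tables of events within 7 days of an injection are optional.

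The cost is extra table programming from data that are already coded and graded, plus some sparse cells in small groups. No visit, procedure or data item changes.

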#### 9.3 Analysis of the Primary Efficacy Variable

A full Statistical Analysis Plan will be created prior to database lock. All post-hoc analyses will be identified and described in the Clinical Study Report. When possible, statistical testing will be applied.

Amendment 7.0: September 22, 2022

#### 9.3.1 Analysis Populations and Sets

The analysis sets for this clinical study are defined in accordance with *ICH E9 Guidance for Industry Statistical Principles for Clinical Trials*. The Full Analysis Set is intended to be the population which is as complete as possible and as close as possible to the intention-to-treat ideal. This is an open label study and not randomized, therefore the Full Analysis Set will include only subjects who have received any study treatment and will be the same as the Safety Population. Analysis sets are described below in Table 12.

